8.1.3 Dose schedule

Insulin glargine/lixisenatide fixed ratio combination (FRC)

The FRC should be self-administered once daily in the morning in the hour (0 to 60 minutes) before breakfast, using Peach Pen or Olive Pen depending on the daily dose of insulin glargine.

Victoza®

Liraglutide (Victoza®) will be administered as per local labelling (such as SmPC in the European Union or PI in the US), continuing the same dose schedule as before randomization. Victoza® can be administered once daily at any time of day, independently of meals.

Byetta®

Exenatide BID (Byetta®) will be administered as per local labelling (such as SmPC in the European Union or PI in the US), continuing the same dose schedule as before randomization. Byetta® can be administered twice daily at any time within the 60 minute period before the morning and evening meal (or two main meals of the day, approximately 6 hours or more apart). Byetta® should not be administered after a meal.

At days of on-site visits, the IMP which is to be administered before breakfast should be self-administered at the investigational site under the observation of site staff.

Bydureon®

Exenatide extended-release (Bydureon®) will be administered as per local labelling (such as SmPC in the European Union or PI in the US), continuing the same dose schedule as before randomization. Bydureon® can be administered once a week at any time of day, independently of meals.

Tanzeum®

Albiglutide (Tanzeum®) will be administered as per local labelling (such as SmPC in the European Union or PI in the US), continuing the same dose schedule as before randomization. Tanzeum® can be administered once a week at any time of day, independently of meals.

Trulicity®

Dulaglutide (Trulicity®) will be administered as per local labelling (such as SmPC in the European Union or PI in the US), continuing the same dose schedule as before randomization. Trulicity® can be administered once a week at any time of day, independently of meals.

Injection site

The IMP should be administered by deep subcutaneous injection, alternating between the left and right anterolateral and left and right posterolateral abdominal wall or thighs or upper arms. Within a given area, location should be changed (rotated) at each time to prevent injection site skin reactions

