8.4 METHOD OF ASSIGNING PATIENTS TO TREATMENT GROUP

Patients will be randomized to one of the two following treatment arms during the 26-week open-label treatment period:

- FRC once daily, or
- Victoza® once daily, Byetta® twice daily, Bydureon® once weekly, Tanzeum® once weekly, or Trulicity® once weekly (continuing whichever therapy they were taking prior to randomization).

The randomization ratio is 1:1. The randomization is stratified by HbA1c (<8%, ≥8%) at screening and GLP-1 receptor agonist subtype at screening (once/twice daily formulations, once weekly formulations).

The randomization and the treatment allocation are performed centrally by an interactive response technology (IRT). The randomized treatment kit number list is generated centrally by Sanofi, and the Study Biostatistician provides the randomization scheme (including stratification) to the IRT. Then, the IRT generates the patient randomization list according to which it allocates treatment groups to the patients.

The IMPs (FRC, or Victoza®, or Byetta®, or Bydureon®, or Tanzeum®, or Trulicity®) will be provided starting at V3 in open-label boxes and are identified with treatment kit numbers.

At the screening visit the Investigator or designee has to contact the IRT center to receive the patient number. The patient identification (patient number) is composed of a 12-digit number containing the 3-digit country code, the 4-digit center code and the 5-digit patient chronological number (which is 00001 for the first patient screened in a center, 00002 for the second patient screened in the same center, etc).

A patient cannot be randomized more than once in the study.

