10.1.2 Open-label randomized treatment period (Week 0 to Week 26)

Patients meeting all inclusion criteria and with no exclusion criteria at the end of the screening period are eligible to be enrolled into the open-label randomized treatment period. The duration of the open-label treatment period for all patients is 26 weeks \pm 5 days from baseline visit (V3, Week 0) to the end of treatment visit (V28, Week 26).

Each patient self-administers IMP once daily from V3 (Week 0) up to the end of the open-label treatment period (V28, Week 26) for the patients treated with FRC or Victoza®, twice daily within 60 minutes prior to a meal for patients treated with Byetta®, and once weekly for patients treated with Bydureon®, Tanzeum®, or Trulicity®. The IMP dose for the patients receiving the FRC will be adjusted according to fasting SMPG values documented in the patient diary ([Section 8.1.4](#)).

Patients randomized in the GLP-1 RA arm continue their treatment during the open-label randomized period as before the randomization.

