11.4.3.2 Compliance

Overall treatment compliance is defined as the actual number of days with IMP injection compared to the planned number of days with IMP injection during the open-label treatment period, up to treatment discontinuation. It is calculated according to the following formula:

For once/twice daily formulation

$$\text{Compliance rate (\%)} = \left[\frac{\text{Total number of days with IMP injection}}{\text{Planned number of days with IMP injection}} \right] \times 100 .$$

For once weekly formulations,

$$\text{Compliance rate (\%)} = \left[\frac{\text{Total number of weeks with IMP injection}}{\text{Planned number of weeks with IMP injection}} \right] \times 100$$

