The number (%) of patients with events reported on Device-related event questionnaire will be summarized for each treatment group along with 2 subcategories, events associated with a clinical event (either symptomatic hypoglycemic event or adverse event) and events not associated with clinical event. The number of events and rates in patient year will also be summarized as appropriate. In addition, a listing of patients with those events will be provided.

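### Device-related event summaries do not allow for injection frequency, which differs between FRC and the mixed control devices, so they cannot separate device performance from number of uses

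*Protocol*

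**What the plan says.** Device-related events are part of the safety endpoints (Protocol 9.2.2). Protocol 10.6.8 gives examples: jamming, partial injection, trouble attaching the needle, pen breakage, mix-up of pens, difficulty with the leaflet, and use error.

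Protocol 11.4.6.2 says that the number (%) of patients with such events "will be summarized for each treatment group along with 2 subcategories", according to whether a clinical event was associated. It then adds: "The number of events and rates in patient year will also be summarized as appropriate". SAP 2.4.5.2 repeats that sentence. Neither document plans a rate per injection or per device.

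The injection schedules differ:
- FRC (Protocol 8.1.3): "The FRC should be self-administered once daily in the morning in the hour (0 to 60 minutes) before breakfast".
- Control (Protocol 8.4): "Victoza® once daily, Byetta® twice daily, Bydureon® once weekly, Tanzeum® once weekly, or Trulicity® once weekly".

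The mix of control products is not fixed. Randomization is only stratified by "GLP-1 receptor agonist subtype at screening (once/twice daily formulations, once weekly formulations", with no quota or expected share. SAP 2.4.5 allows selected safety summaries by this subtype but does not name device events among them.

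**The concern.** Most of the listed device problems can occur only when the device is used, so each injection is an opportunity for an event. The planned denominators are patients and patient-years, and neither reflects how many injections were given. The FRC and control columns will stand side by side in the report. A reader who sees different rates cannot tell whether one device fails more often or is simply used more often.

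The plan already treats weekly products separately elsewhere, with their own exposure formula (Protocol 11.4.3.1), compliance formula (11.4.3.2) and treatment-emergent window (11.4.6.2). The device-event rate has no such adjustment. At stake is whether the table can inform any statement about FRC pens relative to control devices.

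**Working it through.** The documents give no expected device-event rate, so there is no planned figure to reproduce. The check asks what the planned summaries would show if every device had the same failure probability *p* per use.

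**Inputs**
- Uses per patient-year, from the schedules in Protocol 8.1.3 and 8.4: FRC 365; once-daily control 365; twice-daily control 2 × 365 = 730; weekly control 52.
- *w*, the share of all controls on a weekly product, and *b*, the share of all controls on twice-daily exenatide. Neither is stated, so both are varied as assumptions.

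**Patient-year ratio by control device.** The rate is *p* × uses per patient-year, so *p* cancels in the ratio FRC/control:
- weekly: 365/52 ≈ 7
- once daily: 365/365 = 1
- twice daily: 365/730 = 0.5

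**Pooled control arm.** Mean control uses = 365(1 − w − b) + 730b + 52w. The ratio is 365 divided by this.

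| w | b | Mean control uses per patient-year | FRC/control ratio |
|---|---|---|---|
| 30% | 0 | 255.5 + 0 + 15.6 = 271.1 | 1.35 |
| 50% | 0 | 182.5 + 0 + 26 = 208.5 | 1.75 |
| 70% | 0 | 109.5 + 0 + 36.4 = 145.9 | 2.50 |
| 50% | 10% | 146 + 73 + 26 = 245 | 1.49 |
| 10% | 10% | 292 + 73 + 5.2 = 370.2 | 0.99 |
| 30% | 30% | 146 + 219 + 15.6 = 380.6 | 0.96 |

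**Break-even.** The ratio equals 1 when 365b = 313w, that is w ≈ 1.17b. With 10% of controls on twice-daily exenatide, an artificial FRC excess appears once the weekly share passes about 12%. Below that share it is an artificial deficit.

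**Number (%) of patients.** Over 26 weeks there are 182 uses on FRC or a once-daily control, 26 on a weekly product and 364 on a twice-daily one. With an assumed *p* = 0.0005, the chance of at least one event is 1 − (1 − p)^uses:
- FRC or once-daily control: 8.7%
- weekly control: 1.3%
- twice-daily control: 16.6%
- pooled control at w = 50%, b = 0: 0.5 × 1.3% + 0.5 × 8.7% = 5.0%, against 8.7% on FRC

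The lead summary therefore depends on injection frequency in the same way as the rate.

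**With a per-injection denominator.** In the same example both arms show 1,000 × 0.0005 = 0.5 events per 1,000 injections, whatever *w* and *b* are.

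**The case against.** **The analysis is descriptive.** SAP 2.4.5 plans no testing of safety variables, the patient-year rates are optional, and no between-arm comparison of devices is specified. This stands, and it limits the point to how a table is read.

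**Patient-years answer a legitimate question.** If daily injection brings more device problems in a year, that is a real consequence of the regimen. This also stands, and it is why the patient-year rate should be kept.

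**Not every event scales with use.** Difficulty with instructions and pen mix-up may arise once per patient. FRC patients also start new pens, in two strengths, at randomization (Protocol 8.1.2.2), while controls continue a product taken for at least 4 or 6 months before screening (Protocol 7.1). So it would go too far to say that the planned rates mainly measure injection frequency. A per-injection rate has its own distortion too: an event that occurs equally often per patient would look about 7 times as frequent per injection on a weekly device.

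**The subtype breakdown could expose the artefact.** Within the control arm it does separate weekly from daily devices, and FRC patients in both strata use the same daily pens. But the SAP does not commit to it for device events, and it leaves once-daily and twice-daily products pooled.

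**Conclusion.** The point holds as a limitation of interpretation. As planned, the device-event summaries mix device performance with injection frequency, and neither document provides a summary that separates them. With equal failure per use, the patient-year ratio against a single control schedule runs from 0.5 (twice daily) to about 7 (weekly). Against the pooled arm it depends on an unstated mix.

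A reader might infer that FRC pens are bound to show a spurious excess because much of the control arm injects weekly. The documents do not support that. They permit weekly products and stratify on them but give no share, and twice-daily exenatide pushes the ratio the other way. A reader might also infer that the plan tests devices between arms, or that the patient-year rate is invalid. Neither is so.

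The sizes rest on two assumptions: equal failure probability per use, and events that scale with use. The primary endpoint, alpha and power are unaffected. This is a cheap improvement to one descriptive table.

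**What to change.** In SAP 2.4.5.2, and in Protocol 11.4.6.2 if it is amended for other reasons:

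1. Keep the number (%) of patients and the patient-year rate.
2. Add device-related events per 1,000 injections beside them. The compliance derivation in Protocol 11.4.3.2, based on the "actual number of days with IMP injection compared to the planned number of days with IMP injection" and on weeks with injection for weekly products, supplies most of the denominator. Use days with injection for FRC and liraglutide, twice that for twice-daily exenatide, and weeks with injection for weekly products.
3. Show control-arm device events, both number (%) and rates, separately for once-daily, twice-daily and once-weekly devices.

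The cost is SAP wording, one derived denominator and three control columns. There are three downsides to state in the table notes. The twice-daily count assumes two injections on every injection day. Events that do not scale with use make the per-injection rate look high for weekly devices. And no denominator removes the difference in familiarity between new FRC pens and continued control products.

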11.4.6.3 Analyses of laboratory variables

See [Section 9.2.2.3](#).

The number (%) of patients with PCSA at any evaluation during the on-treatment period will be summarized for each clinical laboratory test within each treatment group. The summaries will include patients in the safety population who have at least one laboratory test performed during the on-treatment period and, when required by the definition of the abnormality, with an available baseline value and available laboratory normal range.

Descriptive statistics will be used to summarize the laboratory test results and the changes from baseline by visit and for the last on-treatment value within each treatment group.

Shift tables and other tabular and graphical methods may be used to present the results for laboratory tests of interest.

Listing will be provided with flags indicating the out of laboratory range values as well as the PCSA values.

Drug-Induced Liver Injury

The liver function tests, namely AST, ALT, alkaline phosphatase and total bilirubin are used to assess possible drug induced liver toxicity. The proportion of patients with PCSA values at any post baseline visit by baseline status will be displayed by treatment group for each parameter. The proportion of patients with PCSA values at any post baseline visit will also be displayed by duration of exposure for each treatment group only if a tabulation summary is necessary.

A listing will be provided of possible Hy's Law cases identified by treatment group (eg, patients with any elevated ALT >3 x ULN, and associated with an increase in total bilirubin >2 x ULN) with liver-related TEAEs, ALT, AST, ALP, total bilirubin and the following complementary parameters, if available: Conjugated Bilirubin and Prothrombin Time/International normalized ratio (INR), creatine phosphokinase, serum creatinine, complete blood count, Immunoglobulin M (IgM) antibodies to Hepatitis A virus, IgM antibodies to Hepatitis B core antigen, antibodies to Hepatitis C Virus, and Hepatitis C ribonucleic acid, IgM antibodies to Cytomegalovirus, and IgM

antibodies to Hepatitis E virus, Auto-antibodies: anti-nuclear, anti-deoxyribonucleic acid, anti-smooth muscle, Epstein-Barr virus, Herpes viruses and anti-liver/kidney microsomes.

11.4.6.4 Analyses of vital sign variables

See [Section 9.2.2.4](#).

The number and percentage of patients with PCSA at any evaluation during the on-treatment period will be summarized for each vital sign parameter within each treatment group. The summaries will include patients in the safety population who have at least one parameter to be analyzed during the on-treatment period. When the PCSA definition involves the change from the baseline value, patients need also to have a baseline value to be included in the summaries.

Descriptive statistics will be used to summarize the results for systolic and diastolic blood pressure and heart rate, and the changes from baseline by visit and for the last on-treatment value within each treatment group.

Tabular and graphical methods may be used to present the results for parameters of interest.

Listings will be provided with flags indicating the PCSA values.

11.4.6.5 Analysis of 12 lead ECG status

See [Section 9.2.2.5](#).

A shift table will be provided to present the ECG on-treatment status according to the baseline status within each treatment group.

11.4.6.6 Analyses of anti-drug antibody variables

Analyses of antibody variables will be performed on the safety population (only in patients from the FRC group).

The number and percentage of patients by antibody status will be listed and summarized by visit, as well as the percentage of conversion from negative to positive status from baseline to Week 26 and Week 52. For anti-insulin antibodies, the number and percentage of patients with cross-reactivity to human insulin will also be summarized by visit in anti-insulin glargine positive patients. For anti-lixisenatide antibodies, the number and percentage of patients with cross-reactivity to GLP-1 and glucagon will be summarized by visit in anti-lixisenatide antibody positive patients.

Antibody levels (titer or concentration), as well as respective percentage changes from baseline for anti-insulin antibodies, will be listed and summarized by visit using descriptive statistics by N, geometric mean, coefficient of variation, median, minimum and maximum.

11.5 INTERIM ANALYSIS

No formal interim analysis for efficacy is planned for this study.

The primary analysis of the efficacy and safety will be performed on the data collected during the 26-week randomized treatment period. The timing of this analysis is when the last randomized patient has completed the 26-week randomized treatment period. The results of the primary analysis will not be used to change the conduct of the ongoing study in any aspect.

It is planned to lock the database approximately 4 weeks after Last Patient Last Visit of the randomized treatment period (26 weeks). It is further planned to lock the database approximately 4 weeks after Last Patient Last Visit of the single-arm extension period (extension by further 26 weeks).

12 ETHICAL AND REGULATORY CONSIDERATIONS

12.1 ETHICAL AND REGULATORY STANDARDS

This clinical trial will be conducted by the Sponsor, the Investigator, delegated Investigator staff and Subinvestigator, in accordance with the principles laid down by the 18th World Medical Association Assembly (Helsinki, 1964) and all applicable amendments laid down by the World Medical Association Assemblies, and the International Council for Harmonization (ICH) guidelines for good clinical practice (GCP), all applicable laws, rules and regulations.

This clinical trial will be recorded in a free, publicly accessible, internet-based registry, no later than 21 days after the first patient enrollment, in compliance with applicable regulatory requirements and with Sanofi public disclosure commitments.

12.2 INFORMED CONSENT

The Investigator (according to applicable regulatory requirements), or a person designated by the Investigator, and under the Investigator's responsibility, should fully inform the patient of all pertinent aspects of the clinical trial including the written information giving approval/favorable opinion by the Ethics Committee (IRB/IEC). All participants should be informed to the fullest extent possible about the study, in language and terms they are able to understand.

Prior to a patient's participation in the clinical trial, the written informed consent form should be signed, name filled in and personally dated by the patient or by the patient's legally acceptable representative, and by the person who conducted the informed consent discussion. A copy of the signed and dated written informed consent form will be provided to the patient.

The informed consent form used by the Investigator for obtaining the patient's informed consent must be reviewed and approved by the Sponsor prior to submission to the appropriate Ethics Committee (IRB/IEC) for approval/favorable opinion.

12.3 INSTITUTIONAL REVIEW BOARD/INDEPENDENT ETHICS COMMITTEE (IRB/IEC)

As required by local regulation, the Investigator or the Sponsor must submit this clinical trial protocol to the appropriate IRB/IEC, and is required to forward to the respective other party a copy of the written and dated approval/favorable opinion signed by the Chairman with IRB/IEC composition.

The clinical trial (study number, clinical trial protocol title and version number), the documents reviewed (clinical trial protocol, informed consent form, Investigator's Brochure, Investigator's curriculum vitae [CV], etc) and the date of the review should be clearly stated on the written (IRB/IEC) approval/favorable opinion.

IMP will not be released at the study site and the Investigator will not start the study before the written and dated approval/favorable opinion is received by the Investigator and the Sponsor.

During the clinical trial, any amendment or modification to the clinical trial protocol should be submitted to the IRB/IEC before implementation, unless the change is necessary to eliminate an immediate hazard to the patients, in which case the IRB/IEC should be informed as soon as possible. It should also be informed of any event likely to affect the safety of patients or the continued conduct of the clinical trial, in particular any change in safety. All updates to the Investigator's Brochure will be sent to the IRB/IEC.

A progress report is sent to the IRB/IEC at least annually and a summary of the clinical trial's outcome at the end of the clinical trial.

13 STUDY MONITORING

13.1 RESPONSIBILITIES OF THE INVESTIGATOR(S)

The Investigator is required to ensure compliance with all procedures required by the clinical trial protocol and with all study procedures provided by the Sponsor (including security rules). The Investigator agrees to provide reliable data and all information requested by the clinical trial protocol (with the help of the CRF, Discrepancy Resolution Form [DRF] or other appropriate instrument) in an accurate and legible manner according to the instructions provided and to ensure direct access to source documents by Sponsor representatives.

If any circuit includes transfer of data particular attention should be paid to the confidentiality of the patient's data to be transferred.

The Investigator may appoint such other individuals as he/she may deem appropriate as Subinvestigators to assist in the conduct of the clinical trial in accordance with the clinical trial protocol. All Subinvestigators shall be appointed and listed in a timely manner. The Subinvestigators will be supervised by and work under the responsibility of the Investigator. The Investigator will provide them with a copy of the clinical trial protocol and all necessary information.

